4.0 OBJECTIVES AND ENDPOINTS

Objective	Endpoint
Primary	
By treatment group (alvelestat/placebo):
 
 • Numbers and % of subjects who experience at least 1 treatment-emergent adverse event to Day 60 (Safety Outcome Assessment) • Adverse events of special interest (liver function abnormalities, corrected QT interval, infections, and neutropenia) and clinically significant safety monitoring labs tests to Day 14 (acute treatment period) or EoT • Number and % of subjects that discontinue alvelestat to Day 5 or 10 • Number and % of subjects requiring dose reduction to Day 5 or 10 • Number and % of subjects with AE of headache on prospective questioning and CTCAE severity Grade to Day 5 or 10 • Change in vital signs, EKG, safety laboratory measures to Day 5 or 10 or EOT
Secondary	
By treatment group (alvelestat/placebo), change from baseline to Day 5 or 10 in:
 
 • Blood biomarkers of NETosis (cell-free DNA; citrullinated histone H3; Myeloperoxidase (MPO)-DNA complexes) • Blood biomarkers of inflammation (absolute neutrophil count; absolute lymphocyte count; neutrophil-lymphocyte ratio [NLR], C-Reactive protein, procalcitonin) • Pro-inflammatory cytokines IL-1beta, IL-6, IL-8, TNF-alpha) • Coagulopathy as measured by D-Dimer • Plasma desmosine/isodesmosine

[figure not shown]
Objective	Endpoint

 To explore the effect of alvelestat on pulmonary function 	By treatment group (alvelestat/placebo): 
 Change from baseline to Day 5 or 10, or EoT in SaO₂/FiO₂

 The effect of alvelestat on disease progression 	By treatment group (alvelestat/placebo): 
 Proportion of subjects alive and free of respiratory failure (without need for non-invasive or invasive mechanical ventilation, high flow oxygen, or Extracorporeal Membrane Oxygenation (ECMO) at Day 29

 The effect of alvelestat on clinical outcomes 	By treatment group (alvelestat/placebo): 
 Mortality rate to Day 90 safety endpoint Proportion of subjects alive and free of respiratory failure (without need for non-invasive or invasive mechanical ventilation, high flow oxygen, or ECMO) at Days 5, 10 and 60 Length of hospital stay Length of ICU stay Time to room air (those on supplemental oxygen at Baseline)

 The effect of alvelestat on disease severity 	By treatment group (alvelestat/placebo): 
 Percentage of patients deteriorating (>1 and >2 increase in WHO 9-point ordinal scale*) at Day 5, Day 10, Day 29 and Day 60 Percentage of patients improving (>1 and >2 decrease in WHO 9-point ordinal scale) at Day 5, Day 10, Day 29 and Day 60

 To explore Pharmacokinetics (PK) in patients with COVID-19 	
 Plasma PK (sparse sampling taken pre or 1-2 hours post study drug dosing) in participants randomized to alvelestat.

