This is a Phase Ib/II single-center, 2:1 randomized, blinded, placebo-controlled, parallel group, first in disease study. The objectives are to determine the safety, tolerability and PK and to explore the mechanistic and clinical effect of the NE inhibitor alvelestat, 240mg orally twice per day for 5 or 10 days added to standard of care (SoC) versus placebo added to SoC, in adult patients (≥ 18 years) with COVID-19 respiratory disease.

Objectives and Endpoints:

Objective	Endpoint
Primary	
• To evaluate the safety and tolerability of alvelestat administered twice daily (bid) for 5 or 10 days	
By treatment group (alvelestat/placebo):
 
 • Numbers and % of subjects who experience at least 1 treatment-emergent adverse event to Day 60 (Safety Outcome Assessment) • Adverse events of special interest (liver function abnormalities, corrected QT interval, infections, and neutropenia) and clinically significant safety monitoring labs tests to EoT • Number and % of subjects that discontinue alvelestat to Day 5 or 10 • Number and % of subjects requiring dose reduction to Day 5 or 10 • Number and % of subjects with AE of headache on prospective questioning and CTCAE severity Grade to Day 5 or 10 • Change in vital signs, EKG, safety laboratory measures to Day 5 or 10 or EOT
Secondary	
• To evaluate the effect of alvelestat on blood pharmacodynamic markers of Neutrophil Extracellular Trap (NET) activation, elastase, inflammatory and coagulopathy activity	
By treatment group (alvelestat/placebo), change from baseline to Day 5 or 10 in:
 
 • Blood biomarkers of NETosis (cell-free DNA; citrullinated histone H3; Myeloperoxidase (MPO)-DNA complexes) • Blood biomarkers of inflammation (absolute neutrophil count; absolute lymphocyte count; neutrophil-lymphocyte ratio [NLR], C-Reactive protein, procalcitonin) • Pro-inflammatory cytokines IL-1beta, IL-6, IL-8, TNF-alpha) • Coagulopathy as measured by D-Dimer • Plasma desmosine/isodesmosine
• To explore the effect of alvelestat on pulmonary function	
By treatment group (alvelestat/placebo):
 
 • Change from baseline to Day 5 or 10 or EoT in SaO₂/FiO₂

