2.0 SCHEDULE OF ASSESSMENTS (SOA)

a) For subjects completing treatment at Day 5

Study period	Screening Period	Study Treatment Period (once daily assessment for safety, respiratory support requirement ⁷ , level of hospital care [ward/ICU] and adverse events during hospitalization) ²					Safety and Efficacy Follow Up Period ²		
Visit Name	Screening	Baseline/ Randomize			End of Treatment (EoT) ⁸	Safety Follow Up (FU)	Clinical Outcome Assessment (COA)	Final Safety Follow Up (FU) 2	Mortality Follow Up
Study Day	Day-2 to Day -1 (screening and randomization can be on same day)	Day 1	Day 2	Days 3 and 4	Day 5	Day 10 (+/- 2 days)	Day 29 (+/- 2 days)	Day 60 (+/- 4 days)	Day 90 (+/- 7 days)
Eligibility check	X								
Informed consent	X								
Medical History	X								
Randomization		X							
Physical exam (full at screening, limited thereafter)	X	X	X	X	X	X			
Study Drug dosing		X	X	X	X				
Interim history, concomitant med, and adverse event recording ^{1, 2}	X	X	X	X	X	X	X ⁵	X ⁵	
Prospective headache query		X			X				
Pregnancy test (high sensitivity serum at screening, urine thereafter) ⁹	X					X			
Blood draw (screening and in-study safety monitoring) ^{2, 9}	X	X			X	X			

Visit Name	Screening	Baseline/ Randomize			End of Treatment (EoT)	Safety Follow Up (FU)	Clinical Outcome Assessment (COA)	Final Safety Follow Up (FU) 2	Mortality Follow Up
Study Day	Day-2 to Day -1 (screening and randomization can be on same day)	Day 1	Day 2	Days 3 and 4	Day 5	Day 10 (+/- 2 days)	Day 29 (+/- 2 days)	Day 60 (+/- 4 days)	Day 90 (+/- 7 days)
Blood draw (biomarkers)		X			X				
SaO ₂ /FiO ₂		X	X	X	X				
Blood (PK) ³		X			X ⁶				
EKG ^{2,4}	X	X			X ⁶				
Progression Endpoint (alive and free of respiratory failure, respiratory support level ⁷)					X	X		X ⁵	
Clinical outcomes assessments including WHO ordinal scale assessment		X	X	X	X	X	X	X ⁵	X ^{5,10}

¹ Only SAEs to be collected prior to randomization

² Investigations and examination performed as part of routine clinical assessment of COVID-19 may be used for eligibility and in study safety, adverse event and respiratory support requirement assessment

³ Time of PK and last dose of study medication prior to PK to be recorded in CRF

⁴ EKG to be taken 1-2 hours after study drug dosing when feasible

⁵ Telehealth visit if hospital discharge occurs before scheduled visit

⁶ PK and EKG can be taken on any one of Days 3-5

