⁷ Level of respiratory support determined by need for room air, supplemental oxygen, high flow oxygen, non-invasive ventilation, intubation, mechanical ventilation or ECMO

⁸ Subjects who terminate study Before Day 5 should have EOT assessment and Safety Follow Up assessment 5 days +/- 2 days after last dose of study drug

⁹ If Screening and baseline are within 24 hours the tests do not need to be repeated at Baseline

¹⁰ Clinical outcome assessment of mortality only

b) For subjects extending study drug to Day 10

Study period	Treatment Period			Safety and Efficacy Follow Up Period ²		
	Visit Name	Extension Period	End of Treatment (EoT)	Safety Follow Up	Clinical Outcome Assessment (COA)	Final Safety Follow Up (FU) ⁴
Study Day		Days 6 to 9	Day 10	Day 15 +/- 2 days	Day 29 (+/- 2 days)	Day 60 (+/- 4 days)
Limited Physical exam		X	X	X		
Study Drug dosing		X	X			
Interim history, concomitant med, and adverse event recording ^{1,2}		X	X	X	X ⁵	X ⁵
Prospective headache query			X			
Pregnancy test (urine)				X		
Blood draw (in-study safety monitoring) ²		X	X	X		
Blood draw (biomarkers)			X			
SaO ₂ /FiO ₂		X	X	X		
EKG ^{2,4}			X	X ⁶		
Progression Endpoint (alive and free of respiratory failure, respiratory support level ⁷)			X			X ⁵
Clinical outcomes assessments including WHO ordinal scale assessment		X	X	X	X ⁵	X ⁵ X ^{5,8}

¹ Only SAEs to be collected prior to randomization² Investigations and examination performed as part of routine clinical assessment of COVID-19 may be used for eligibility and in study safety, adverse event and respiratory support requirement assessment³ Time of PK and last dose of study medication prior to PK to be recorded in CRF⁴ EKG to be taken 1-2 hours after study drug dosing when feasible⁵ Telehealth visit if hospital discharge occurs before scheduled visit⁶ PK and EKG can be taken on any one of Days 3-5⁷ Level of respiratory support determined by need for room air, supplemental oxygen, high flow oxygen, non-invasive ventilation, intubation, mechanical ventilation or ECMO⁸ Clinical outcome assessment of mortality only

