- **A follow-up period** from Day 5 or 10/EoT to Day 90. This is for safety testing to end of systemic drug exposure (Day 10 for 5-day study, Day 15 for 10-day study or 5 days after EoT), to Day 60 for longer term safety and to Day 90 for mortality data collection, for the Clinical Outcome Assessments (COA) to Day 60) and mortality (Day 90). Visits after Day 10 or Day 15 (or 5 days +/- 2 days after last dose), may be by telehealth visits. Adverse events, vital signs, respiratory support and concomitant medications that may be part of routine clinical care will be collected daily during hospitalization and to the Day 29 and Day 60 assessments (may be collected by telehealth call).

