9.5.3 Adverse Events of Special Interest

Some AEs, regardless of their severity or outcome, will be expedited due to the relevance for subject safety or study treatment safety profile. These events should be reported to safety reporting group within 24 hours, as indicated in [Appendix 4](#). The AESIs for alvelestat are:

- Liver function abnormalities defined as:
 - a) Any occurrence of (i) ALT or AST elevations $>5 \times$ ULN or (ii) ALT or AST $>3 \times$ ULN and total bilirubin $>2 \times$ ULN or INR >1.5 or the appearance of worsening fatigue, nausea, vomiting, RUQ pain/tenderness, fever, rash, or eosinophilia.
 - b) Any occurrence of $<5 \times$ ULN or ALT or AST $<3 \times$ ULN and total bilirubin $<2 \times$ ULN where the tests have been repeated within 48 to 72 hours and the elevation confirmed on at least 2 separate occasions.

For participant safety and to ensure that the hepatotoxic potential of the study treatment to be determined, a standardized procedure for identification, monitoring, and evaluation of liver events must be followed as outlined in [Section 9.4.4](#) and [Section 8.1](#).

- EKG

If a study subject experiences any of the following cardiovascular events, the event should be reported immediately as an AESI and the study treatment discontinued:

- a) Absolute QTcF >500 ms or >60 ms increase from baseline.
- b) Any clinically significant cardiac abnormality on EKG.
- Infection

Any new infection that requires the use of systemic antimicrobial treatment (antibiotics, anti-viral, anti-fungal, or anti-mycobacterial) should be investigated with clinically relevant diagnostic tests.

- Neutropenia

Absolute neutrophil count less than or equal to 500 per μ L on 2 consecutive repeat tests within 48 to 72 hours.

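### The primary AESI and safety-laboratory component has two stated windows, and stopping it at end of treatment leaves out the safety follow-up draw that the protocol schedules

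*Protocol*

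**What the plan says.** The second primary bullet covers AESIs (liver, QTc, infection, neutropenia) and clinically significant safety laboratory results. It appears in three current places:

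- Protocol Section 4.0: "clinically significant safety monitoring labs tests to Day 14 (acute treatment period) or EoT".
- Protocol synopsis: "clinically significant safety monitoring labs tests to EoT".
- SAP Table 3 (Section 6.2): the same wording as the synopsis.

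The sixth primary bullet has a similar end point: "Change in vital signs, EKG, safety laboratory measures to Day 5 or 10 or EOT".

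Protocol Section 5.1 gives the purpose of early follow-up as "safety testing to end of systemic drug exposure (Day 10 for 5-day study, Day 15 for 10-day study or 5 days after EoT". Both Schedules of Assessments place a safety blood draw at that visit. For patients who stop early, a footnote to the 5-day schedule says: "Subjects who terminate study Before Day 5 should have EOT assessment and Safety Follow Up assessment 5 days +/- 2 days after last dose".

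Section 9.5.3 defines the neutropenia AESI by a low count "on 2 consecutive repeat tests within 48 to 72 hours". Part (b) of its liver definition also needs a repeat within that interval.

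**The concern.** Safety and tolerability is the trial's only primary objective, and this bullet carries the events the protocol singles out for attention. Two windows for it allow two different counts from the same data. Section 4.0 also does not say whether the earlier or the later of Day 14 and EoT applies.

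The shorter window also sits badly with the design. Follow-up testing exists to cover the time until the drug has cleared, yet a result from that visit would not count in the component it serves. Patients who stop early have the earliest EoT and so the shortest window, and some of them will have stopped because of a suspected safety problem.

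The groups are small, so one patient matters. With the protocol's 10 alvelestat and 5 placebo patients, one reclassified patient moves a group rate by 1/10 = 10 or 1/5 = 20 percentage points. With the SAP's 7 to 8 per arm, it moves by 1/8 = 12.5 to 1/7 = 14.3 points.

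**Working it through.** The plan gives no figure to reproduce. The check is calendar arithmetic on the protocol's Schedules of Assessments.

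**Inputs**

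- 5-day course (schedule a, row "Blood draw (screening and in-study safety monitoring"): post-baseline draws at Day 5 (EoT) and Day 10 ± 2.
- 10-day course (schedule b, row "Blood draw (in-study safety monitoring"): draws in Days 6 to 9, at Day 10 (EoT) and at Day 15 ± 2, added to the Day 5 draw from schedule a.
- Early stoppers: EoT assessment, then safety follow-up 5 ± 2 days after last dose.
- Repeat interval for neutropenia and liver definition (b): 48 to 72 hours, that is 2 to 3 days.

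**Step 1. Does Day 14 match anything?** Treatment ends on Day 5 or Day 10, and safety follow-up is nominally Day 10 or Day 15. No treatment end or scheduled visit is set at Day 14. Because EoT is never planned after Day 10, an earlier-of reading of Section 4.0 reduces to EoT, and a later-of reading makes it Day 14 for everyone.

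**Step 2. Which draws fall inside each window?**

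| Course | Safety follow-up | To EoT | To Day 14 |
|---|---|---|---|
| 5-day | Day 10 ± 2 = Days 8 to 12 | Keeps Day 5, leaves out follow-up: 1 of 2 post-baseline draws | Keeps both, since 12 < 14 |
| 10-day | Day 15 ± 2 = Days 13 to 17 | Leaves out follow-up | Includes follow-up only if drawn on Day 13 or 14; misses nominal Day 15 |

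I give no fraction for the 10-day course, because the schedule has a single column for Days 6 to 9 and does not say how many draws that means.

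For an illustrative patient whose last dose is on Day 2, follow-up falls on Day 2 + 5 ± 2 = Days 5 to 9, after EoT.

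**Step 3. When is an abnormality at the EoT draw confirmed?**

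- Non-extender, first seen Day 5: 5 + 2 to 5 + 3 = Days 7 to 8, after EoT on Day 5.
- Extender, first seen Day 10: 10 + 2 to 10 + 3 = Days 12 to 13, after EoT on Day 10.
- Extender, first seen Day 5: Days 7 to 8, before EoT on Day 10, so inside the window.

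Neither document says whether an AESI that needs confirmation is dated by its first abnormal value or by the confirming test. Under the second convention, the first two cases fall outside a window that ends at EoT.

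**Step 4. Do the analysis sections settle the window?** Protocol Section 10.3.1 tabulates AESIs and summarises laboratory values by visit, with no end date for either. SAP Table 8 lists no AESI or laboratory table. Table 3 is therefore the SAP's only statement of the window for this component.

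**The case against.** The strongest case against is that little depends on this. A reader might infer that post-EoT results are discarded, or that AESI and laboratory tables are cut at EoT. The documents do not support that. Section 10.3.1 sets no such limit, and the Day 10 and Day 15 follow-ups are study visits with a safety draw. Adverse events are collected to Day 60, clinically relevant laboratory changes are recorded as adverse events (Section 9.4.4), and the first primary bullet counts treatment-emergent events to Day 60. A clinically significant transaminase rise on Day 10 can still count there. All of this stands, and it limits the consequence.

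Two other strong readings also fail. It is not true that any Day 5 abnormality can be confirmed only after EoT: for extenders the repeat falls inside the window, and liver definition (a) carries no 48 to 72 hour repeat. Nor do both cut-offs lose the follow-up visit in both courses: Day 14 always includes the 5-day course's visit.

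It is also fair to say that an on-treatment AESI window beside a Day 60 adverse-event window is a legitimate choice, and that this is an unpowered pilot with descriptive safety tables and full listings.

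Two things remain. The three statements of one primary component disagree in current text; this does not rest on the amendment log. And the Day 60 count is no substitute, because it counts patients with any event: a patient who already has another adverse event is counted once, and a late AESI leaves that number unchanged.

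**Conclusion.** The point holds as an inconsistent, and for its purpose too short, window for one primary safety component. It should be fixed, but it does not threaten the trial's data or its overall safety reporting.

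Its size is one scheduled safety draw per patient left out of this component under the EoT reading. That is 1 of 2 post-baseline draws in the 5-day course and the Day 15 draw in the 10-day course. Under the Day 14 reading, only the 10-day course is affected, and only when the visit falls on Day 15 or later.

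The judgement that EoT is too short rests on Section 5.1's own account of what the follow-up testing is for. The confirmation problem depends on the dating convention, which the documents leave open. How many patients would be reclassified cannot be known from the plan.

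**What to change.** In the protocol synopsis, Section 4.0 and SAP Table 3, give this component one identical analysis window: first dose through the scheduled safety follow-up visit (Day 10 ± 2 for the 5-day course, Day 15 ± 2 for the 10-day course, or 5 ± 2 days after last dose for early stoppers). Add an on-treatment (to EoT) column if wanted. State that an AESI needing a confirmatory test is dated by the first abnormal value.

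Bring the laboratory part of the sixth primary bullet into line in the same three places. The EKG part is a separate matter, because the 5-day schedule has no EKG at Day 10.

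The cost is wording: two bullets in three places and one dating rule. The draws are already scheduled, so no visit, sample or procedure is added. The change should be made before database lock and the Day 60 unblinding, so that the window is chosen without sight of the results.

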6.1 Inclusion Criteria

Participants are eligible to be included in the study only if ALL of the following criteria apply:

Type of Participant and Disease Characteristics

- Male or Female
- Age ≥ 18 years
- Proven SARS-CoV-2 infection (confirmed by PCR from a nasopharyngeal or lower respiratory tract sample or antigen testing from a nasal sample)
- A score of Grade 3 to 5 on the WHO 9-point Ordinal Scale
- Male participants must agree to use a highly effective contraception as detailed in [Appendix 5](#) during the treatment period and for at least 4 days after the last dose of study treatment and refrain from donating sperm during this period
- Female participants are eligible to participate if not pregnant; not breastfeeding; and at least one of the following conditions is met:
 - Not a woman of childbearing potential as defined in [Appendix 5](#)

OR

- A woman of childbearing potential who agrees to follow the contraceptive guidance in [Appendix 5](#). During the treatment phase and for at least 4 days after the last dose of study medication
- Capable of giving signed informed consent which includes a commitment to comply with the requirements and restrictions listed in the informed consent form (ICF) and within this protocol.

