9.1 Key Screening Assessments

- SARS-CoV-2 PCR testing or SARS-CoV-2 antigen testing (routine diagnostic test used for diagnosis of current illness to be used, no additional test required). It is recognized this may have been performed in the period prior to the screening period.
- Laboratory testing performed for clinical management may be used for screening assessment if obtained within 3 days of planned randomization.
- EKG performed for clinical management may be used for screening assessment if obtained within 7 days of planned randomization.

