9.3.2 WHO 9-Point Ordinal Scale

Each assessment will be recorded as a number in the CRF based on the status categories below. Where possible the timing of each assessment should be similar (i.e. morning or evening throughout)

0. Uninfected, no clinical or virological evidence of infection
1. Ambulatory, no limitation of activities
2. Ambulatory, limitation of activities
3. Hospitalized – mild disease, no oxygen therapy
4. Hospitalized – mild disease, oxygen by mask or nasal prongs
5. Hospitalized – severe disease, noninvasive ventilation or high flow oxygen
6. Hospitalized – severe disease, intubation and mechanical ventilation
7. Hospitalized – severe disease, ventilation and additional organ support – vasopressors, renal replacement therapy, extracorporeal membrane oxygenation
8. Death

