	
ventilation, high flow oxygen, or ECMO) at Days 5, 10 and 60
 
 • Length of hospital stay • Length of ICU stay 
Time to room air (those on supplemental oxygen at Baseline)

The effect of alvelestat on disease severity
	
By treatment group (alvelestat/placebo):
 
 • Percentage of patients deteriorating (>1 and >2 increase in WHO 9-point ordinal scale*) at Day 5, Day 10, Day, Day 29 and Day 60 
Percentage of patients improving (>1 and >2 decrease in WHO 9-point ordinal scale) at Day 5, Day 10, Day 29 and Day 60

To explore Pharmacokinetics (PK) in patients with COVID-19
	
Plasma PK (sparse sampling taken pre or 1-2 hours post study drug dosing) in participants randomized to alvelestat.

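### The WHO improvement responder set at a fall of more than 2 points needs score 0 from entry score 3, which no scheduled test can document, and SAP 8.4.2 analyses a different threshold

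*Protocol*

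**What the plan says.** Protocol 6.1 admits patients with "A score of Grade 3 to 5 on the WHO 9-point Ordinal Scale". Protocol 4.0, in the disease-severity row, lists "Percentage of patients improving (>1 and >2 decrease in WHO 9-point ordinal scale) at Day 5, Day 10, Day 29 and Day 60", together with the matching deterioration endpoint (increases of more than 1 and more than 2). The synopsis and SAP Table 3 carry the same thresholds.

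On the scale in Protocol 9.3.2, score 0 is "Uninfected, no clinical or virological evidence of infection", score 1 is "Ambulatory, no limitation of activities" and score 2 is "Ambulatory, limitation of activities". For SARS-CoV-2 testing, Protocol 9.1 relies on the routine diagnostic test, with "no additional test required". Neither Schedule of Assessments table, the outcome data list in Protocol 9.3, nor Appendix 2 includes a later SARS-CoV-2 test. Later visits may be by telehealth.

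Protocol 7.2 does not stratify randomization. Protocol 10.3.2 reports responders as counts and percentages. SAP 6.1 counts any fall of at least one point as improvement and ties discharge to a score of 1 or 2. SAP 7.4 treats a last score of 1 or 2 as recovered. SAP 8.4.2 and Table 11 analyse improvement by one and by two categories at Days 10 and 29.

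**The concern.** A change-score responder on a bounded scale asks for a different end state from each starting score. Here the range of entry scores meets the bottom of the scale. The mildest entrants qualify only at a score that the scheduled data cannot establish, and a patient in a worse final state can be counted as a success while one in a better state is not. The study is meant to look for clinical signals in 15 patients, so an endpoint that misclassifies the best realistic outcome of one entry group loses information the trial can ill afford. The threshold also differs between the endpoint definition and the SAP's analysis section, so two analysts could report different results under the same label.

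**Working it through.** The documents give no expected response rate or power for this endpoint, so there is no figure to reproduce.

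**1. Qualifying scores.** Scores are whole numbers, so a change of more than 2 means at least 3 points and a change of more than 1 means at least 2. Improvement by more than 2 needs follow-up score ≤ baseline − 3; by more than 1, ≤ baseline − 2. Deterioration by more than 2 needs ≥ baseline + 3.

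| Baseline | Fall >2 | Fall >1 (same as two categories) | Rise >2 |
|---|---|---|---|
| 3 | 0 | 0-1 | 6-8 |
| 4 | 0-1 | 0-2 | 7-8 |
| 5 | 0-2 | 0-3 | 8 (death only) |

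**2. Can score 0 be documented?** Its definition includes the absence of virological evidence. No repeat test is scheduled, and no rule says whether an untested, symptom-free patient scores 0 or 1. Because the SAP treats discharge and recovery as 1 or 2, a discharged WHO 3 entrant scored on that basis falls by at most 3 − 1 = 2 and misses the >2 threshold.

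**3. Two patients compared.** Baseline 3, home without limitation: 3 − 1 = 2, non-responder. Baseline 5, home with limitation: 5 − 2 = 3, responder. The second patient ends in the worse state.

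**4. Dilution.** Assume a share f of entrants at WHO 3, none ever recorded as 0. The highest attainable response is 1 − f, and a difference D among WHO 4-5 entrants becomes D(1 − f) overall. With D = 40 points (assumed 80% v 40%):

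| Assumed f | Ceiling | Overall difference | Fisher exact power, 10 v 5 |
|---|---|---|---|
| 0% | 100% | 40 points | 0.21 |
| 20% | 80% | 32 points | 0.14 |
| 33% | 67% | 27 points | 0.11 |
| 50% | 50% | 20 points | 0.06 |

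**5. Chance imbalance in the WHO 3 share.** The SD of the between-arm difference in share is √[f(1 − f)(1/10 + 1/5)]: 0.219 at f = 0.2 and 0.274 at f = 0.5. With the SAP's 7-8 per arm the last bracket is 1/7 + 1/8 = 0.268, giving 0.207 and 0.259. Exactly (hypergeometric, 10 v 5), with 3, 5 or 7 WHO 3 entrants among 15, the arms differ by at least 30 points in that share with probability 0.51, 0.25 or 0.28; these values do not fall steadily because few splits are possible. These are spreads of the baseline share, not of the response.

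**6. How much of the response variance is baseline?** With WHO 3 response fixed at 0 and other rates assumed: for equal thirds at baseline, 12.5% if WHO 4/5 respond at 30%/30%, 44% at 50%/80% and 56% at 60%/90%. For a 20/60/20 mix, the figures are 8%, 27% and 35%.

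**7. Definition against analysis.** Protocol 4.0 and SAP Table 3: more than 1 and more than 2, at Days 5, 10, 29 and 60, with deterioration. SAP 8.4.2 and Table 11: one and two categories, Days 10 and 29, with no matching deterioration proportion. Only the protocol's >1 and the SAP's two categories coincide.

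**The case against.** The best defence is that the endpoint is exploratory, secondary and unpowered, and that the SAP does not carry the >2 rule into its analysis. On the two-category reading a WHO 3 entrant qualifies at score 1 with no virology, and the > sign may have been meant as at least. That is plausible but is an inference; Table 3 still states the strict rule, so the conflict remains. The SAP also shows baseline WHO score by arm (Table 6), adjusts the WHO change score for baseline (8.4.3) and plots scores by baseline (Figure 3). These make the mix visible but do not repair the responder percentage.

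Three stronger readings are tempting and are not supported:

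- A reader might infer that response is impossible from WHO 3. Score 0 is on the scale, and a clinician might record it; what is missing is a scheduled test and a 0-versus-1 rule. Footnote 2 of the Schedule of Assessments allows routine investigations for several purposes but does not name WHO scoring.
- A reader might infer that the endpoint simply measures baseline mix. Allocation is random, so mix brings noise and dilution, not bias, and WHO 4 and 5 entrants can still show an effect. Baseline explains all the response variance only if every one of them responds. Nor does baseline inflate the SD of the crude difference: any binary endpoint with a 20-50% overall rate has the same 22-27 points at 10 v 5.
- A reader might infer that the arm with sicker patients looks better. The required end state is least strict from WHO 5, but those patients start sicker, and the documents give no response rates by entry score.

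**Conclusion.** The point holds as a defect of definition. Under the stated >2 rule, the best outcome that scheduled data can support for a WHO 3 entrant counts as failure, a worse final state counts as success from WHO 5, and the matching deterioration rule counts only death from WHO 5. The endpoint section and the SAP analysis section use different thresholds and days.

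The arithmetic on qualifying scores rests on the documents alone. The effect on the result does not: the 32-20 point range assumes 20-50% WHO 3 entrants, none scored 0, and a 40-point effect elsewhere. With few WHO 3 entrants the dilution is small. The 10 v 5 split is the protocol's; the SAP's 1:1 allocation conflicts with it and needs separate reconciliation. Because the endpoint is exploratory, this does not threaten the primary safety objective, but it should be corrected while only wording is at stake.

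**What to change.** - Score 0 and 1 as one category, because follow-up virology is not collected.
- Drop the strict >2 improvement responder. Use one threshold that every entrant can reach: improvement of at least 2 categories, alive with WHO ≤2, or both. Report at Days 5, 10, 29 and 60 with all randomized patients in the denominator.
- Replace the >2 increase with WHO ≥6 or dead at the same days.
- Tabulate all of these by baseline WHO score. This is needed because the replacements also depend on baseline: WHO ≤2 is one step from WHO 3 and three from WHO 5, WHO ≥6 is the reverse, and two categories from WHO 5 still admits a patient in hospital off oxygen.
- Make the wording identical in the protocol synopsis and 4.0 and in SAP Table 3, 8.4.2 and Table 11.

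The WHO score is already scheduled at these days, so the cost is wording and a few table rows. One exploratory responder definition changes, and alive with WHO ≤2 partly overlaps the SAP's recovery analysis.
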